8.3.1. Adverse Events

An AE is any untoward medical occurrence in a patient or clinical investigation participant and that does not necessarily have a causal relationship with this treatment. An AE can therefore be any unfavorable and unintended sign (including an abnormal laboratory finding), symptom or disease temporally associated with the use of a medicinal (investigational) product whether or not related to the medicinal (investigational) product. In clinical studies, an AE can include an undesirable medical condition occurring at any time, including baseline or washout periods, even if no study treatment has been administered.

Adverse events will be coded using Medical Dictionary for Regulatory Activities (MedDRA) Version 25.1.

A TEAE is defined as an AE with onset on or after the first dose of SAGE-718- - either in the parent study or within this protocol and on or after the ICF sign off date. For more clarification, a TEAE is defined as below:

- For Placebo rollover participants from parent study: TEAE is defined as an AE with onset on or after the first dose of SAGE-718 in this protocol.

- For SAGE-718 rollover participants from the parent study: TEAE is defined as an AE with onset on or after the ICF sign off in this protocol.

Pre-treatment AE is defined as below.

- For Placebo rollover participants from parent study: Pre-treatment AE is defined as an AE with onset before the first dose of SAGE-718 in this protocol and after ICF sign off date in this protocol or ongoing AE from parent study.
- For SAGE-718 rollover participants from the parent study: Pre-treatment AE is defined as an AE with onset after ICF sign off date in this protocol and before the first dose date of IP in the current protocol.

On-treatment TEAE:

- For Placebo rollover participants from parent study: On-treatment TEAE is defined as an AE with onset on or after the first dose of SAGE-718 in this protocol and on or before IP last dose date + 30 days (Note that time does not matter for the end of this period. i.e. if AE occurred after the last dose but on the same date of last dose, it is considered as on-treatment TEAE).
- For SAGE-718 rollover participants from the parent study: On-treatment TEAE is defined as an AE with onset on or after first IP dose date/time and on or before IP last dose date + 30 days.

Post-treatment TEAE: AE onset date on or after IP last dose date + 31 days.

The analysis of AEs will be based on the concept of TEAEs. If the date of an adverse event is incomplete and an unambiguous determination could not be made with respect to its onset time versus the first dose of study drug and/or last dose of study drug, the adverse event will be assumed to be a TEAE. For imputation of missing AE dates, please refer to [Appendix B](#).

An overall summary of TEAEs will include the number and percentage of participants in the following categories:

- Any TEAEs
- Any TEAEs (Pre-treatment, On-treatment, Post-treatment)
- TEAEs by maximum Severity (severe>moderate>mild)
- Any TEAEs related to IP
- Any TEAEs leading to death
- Any TEAEs leading to IP discontinuation
- Any TEAEs leading to withdrawal from the study
- Any TEAEs leading to IP interruption
- Any serious TEAEs
- Any serious TEAE related to IP

- Any serious TEAE leading to IP discontinuation
- Any serious TEAE leading to withdrawal from the study

Incidence of TEAEs in following categories will be provided by System Organ Class (SOC) and Preferred Term (PT). A participant is counted only once under each SOC and PT in case of multiple occurrences of the same AE. These tables will be sorted by decreasing frequency of SOC in overall group, then alphabetically first within SOC then within PT.

- Any TEAE
- TEAEs by maximum severity
- TEAEs by relationship
- Serious TEAEs
- TEAEs leading to IP discontinuation
- TEAEs leading to withdrawal from the study
- TEAEs leading to IP interruption

Additionally, incidence of TEAEs will be summarized by PT. Most common TEAEs reported >5% in any cohort will also be summarized by PT.

For maximum severity, participants will be counted only once within each SOC and PT at the maximum severity in the following order: severe > moderate > mild; an AE with missing severity will be omitted from severity presentation and will not be imputed. For relationship to IP, participant will be counted only once within each SOC and PT at the strongest relationship to IP in the following order: related > not related; an AE with relationship missing is treated as related. For seriousness, an AE with missing seriousness will not be included in the summary tables. The incidences will be sorted by descending frequency of SOC and then, within a SOC, by descending frequency of PT based on overall group, and in alphabetical order of PT if the incidence within a PT is a tie.

All TEAEs through the end of the study will be listed by participant. Separate listings of pre-treatment AE, treatment-emergent serious adverse event (SAE), TEAEs leading to IP discontinuation, TEAEs leading to withdrawal from the study, TEAEs leading to IP interruption, and death will be provided.

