- ^o Only applicable for direct rollover participants that did not provide sample(s) in the parent study.

- w At scheduled clinic visits, participants will self-administer IP in the clinic under the supervision of study staff. All scheduled safety assessments will be conducted prior to dosing and all scheduled cognitive tests will be administered post dosing. (All Day 1 assessments should be done predose).
- x Study staff will dispense sufficient IP for the participant to take daily at home until the next scheduled visit.
- y Participants will bring all used packaging and unused IP to the clinic at each visit for study staff to review and document.
- z AEs/SAEs will be collected beginning with completion of 718-CIH-301 informed consent through end of study participation. Documented ongoing AE/SAE from parent studies will be collected to follow through resolution.
- aa All medications, supplements, procedures, and therapies taken within 8 weeks prior to obtaining 718-CIH-301 informed consent will be recorded through the end of the study. All medications, supplements, procedures, and therapies used to treat Huntington's Disease or to treat or prevent COVID, regardless of timing will be recorded through the end of the 718-CIH-301 study.

Table 4: Schedule of Assessments: Additional Visits for 718-CIH-301 v2 Completers

Assessments	Re-Qualification Visit ^{a, b}		Post Re-Qualification Safety Check-in
	Up to 28 days prior to Next Scheduled Study Treatment Visit	Next Scheduled Study Treatment Visit (See Table 5) ^c	30 days (± 7 days) after Next Scheduled Study Treatment Visit
Informed re-consent ^d	X		
Reconfirm inclusion/exclusion criteria ^e	X		
Interim medical history ^f	X		
Optional participant training ^g	X		
Body weight	X		
Body height	X		
Vital signs (including orthostatics) ^h	X		X
Physical examination ⁱ	X		X
Serology test ^j	X		
12-lead ECG ^k	X		X
Safety laboratory assessments ^l	X		X
Urine drug test	X		
Alcohol breath test	X		
Cigarette/tobacco use assessment	X		
Pregnancy test ^m	X		
<hr/>			
C-SSRS (Since Last Visit)	X		X
IP self-administration ⁿ			X
IP adherence monitoring			X
AEs/SAEs ^o	X		X
Prior and concomitant medications and procedures/therapies ^p	X		X

Abbreviations: AE = adverse event; C-SSRS = Columbia–Suicide Severity Rating Scale; ECG = electrocardiogram; eCRF = electronic Case Report Form; HIV = human immunodeficiency virus; IP = investigational product; SAE = serious adverse event.

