6. STUDY OBJECTIVES AND ENDPOINTS

Objectives	Endpoints
Primary	
To evaluate the safety and tolerability of SAGE-718 softgel lipid capsule in participants with Huntington's Disease (HD)	
• Proportion of participants experiencing treatment-emergent adverse events (TEAEs) and severity of TEAEs• Number of participants who withdraw due to adverse events (AEs)• Change from Baseline in vital signs, clinical laboratory parameters, electrocardiograms (ECGs), and Columbia Suicide Severity Rating Scale (CSSRS) responses.
Other	

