12.2. Adverse and Serious Adverse Events

12.2.1. Adverse Event Definition

An AE is any untoward medical occurrence in a patient or clinical investigation participant administered a pharmaceutical product and that does not necessarily have a causal relationship with this treatment. An AE can therefore be any unfavorable and unintended sign (including an abnormal laboratory finding), symptom or disease temporally associated with the use of a medicinal (investigational) product whether or not related to the medicinal (investigational) product. In clinical studies, an AE can include an undesirable medical condition occurring at any time, including baseline or washout periods, even if no study treatment has been administered.

A TEAE is defined as an AE with onset after the start of IP, or any worsening of a pre-existing medical condition/AE with onset after the start of IP and throughout the study. The term IP includes any Sage IP, a comparator, or a placebo administered in a clinical study.

Laboratory abnormalities and changes from baseline in vital signs, and ECGs are considered AEs if they result in discontinuation or interruption of IP, require therapeutic medical intervention, meet protocol specific criteria (if applicable) or if the investigator considers them to be CS. Any abnormalities that meet the criteria for an SAE should be reported in an expedited manner.

Laboratory abnormalities and changes from baseline in vital signs and ECGs that are clearly attributable to another AE do not require discrete reporting (eg, electrolyte disturbances in the context of dehydration, chemistry, and hematologic disturbances in the context of sepsis).

All AEs that occur after any participant has signed the informed consent and throughout the duration of the study, whether or not they are related to the study, must be reported to Sage.

Participants who discontinue the IP due to an AE, regardless of investigator-determined causality, should be followed until the event is resolved, considered stable, or the investigator determines the event is no longer clinically significant. Any AEs that are unresolved at the participant's last AE assessment in the study are followed up by the investigator for as long as medically indicated, but without further recording in the eCRF. The sponsor or its representative retains the right to request additional information for any patient with ongoing AE(s)/SAE(s) at the end of the study, if judged necessary.

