13.6.1. Adverse Events

AEs/SAEs will be collected beginning with completion of ICF through end of study participation. For gap and direct rollover participants, ongoing AE/SAE(s) from parent studies will be followed for resolution through the end of 718-CIH-301 participation.

For 718-CIH-301 v2 Completers, AEs/SAEs will be collected from the time of informed consent for 718-CIH-301 Protocol Version 3 or higher through end of study participation. Documented ongoing AEs/SAEs from participation under 718-CIH-301 Protocol Version 2 or prior will be followed for resolution through end of study participation.

AEs will be coded using Medical Dictionary for Regulatory Activities (MedDRA™) Version 25.0 or higher. A TEAE is defined as an AE with onset after the first dose of IP, either in the parent study or within this protocol and on or after the ICF sign off date. The analysis of AEs will be based on the concept of TEAEs. The incidence of TEAEs will be summarized by system organ class and preferred term. In addition, summaries will be provided by intensity (mild, moderate, severe) and by causality (related, not related) to IP.

Any TEAEs leading to discontinuation of IP or withdrawal from the study and any treatment-emergent SAEs will be summarized.

All AEs and SAEs (including those with onset or worsening before the start of IP) through the end of the study will be listed.

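### Protocol 12.2.1 counts worsening as treatment-emergent, but Protocol 13.6.1 and SAP 8.3.1 count onset only, so a carried-over AE that worsens on SAGE-718 can drop out of the primary TEAE results

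*SAP*

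**What the plan says.** The first primary endpoint in Protocol section 6 is "Proportion of participants experiencing treatment-emergent adverse events (TEAEs) and severity of TEAEs". Treatment-emergent is defined in three places.

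- **Protocol 12.2.1** counts new onsets after the start of IP, and also "any worsening of a pre-existing medical condition/AE with onset after the start of IP and throughout the study". It adds that "The term IP includes any Sage IP, a comparator, or a placebo administered in a clinical study".
- **Protocol 13.6.1**, the analysis section, has no worsening limb: "A TEAE is defined as an AE with onset after the first dose of IP, either in the parent study or within this protocol". It also requires that the onset does not precede 301 consent.
- **SAP 8.3.1** is also by onset only. For placebo rollovers a "TEAE is defined as an AE with onset on or after the first dose of SAGE-718 in this protocol". For SAGE-718 rollovers the onset must be on or after 301 consent.

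For placebo rollovers, SAP 8.3.1 places in the pre-treatment class any AE that began "before the first dose of SAGE-718 in this protocol and after ICF sign off date in this protocol or ongoing AE from parent study". The matching definition for SAGE-718 rollovers covers only onsets between 301 consent and first 301 dose, and does not mention ongoing parent AEs.

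On carried-over events, Protocol Table 3, footnote z, says: "Documented ongoing AE/SAE from parent studies will be collected to follow through resolution". Protocol 12.1 leaves the recording of parent-study AEs to the eCRF Completion Guidelines. SAP 6.1 lists the changes from the protocol; the TEAE definition is not among them. It also says that the de novo cohort was not enrolled.

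**The concern.** With no de novo participants, everyone in the Safety Set comes from a parent study. Exclusion criteria 21 and 22 bar only ongoing IP-related SAEs and ongoing AEs judged likely to interfere with conduct or compliance. Other ongoing AEs come in with the participant.

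For a placebo rollover, 301 is the first exposure to SAGE-718. If a mild parent-study AE becomes severe in that period, Protocol 12.2.1 would count it. An onset-only rule need not. SAP 8.3.1 bases the AE analysis on TEAEs, so an event outside the definition is missing from the incidence, maximum-severity, serious-TEAE and TEAE-discontinuation tables together. The omission can only lower the counts.

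**Working it through.** **Step 1. Follow one event through each definition.** Take an AE that starts in the parent study, is ongoing at 301 consent, worsens on SAGE-718 in 301, and keeps its parent onset date.

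| Rule | Result |
|---|---|
| Protocol 12.2.1 | TEAE, through the worsening limb |
| Protocol 13.6.1 | Not a TEAE: onset precedes 301 consent |
| SAP 8.3.1, placebo rollover | Not a TEAE: onset precedes the first 301 dose. Pre-treatment AE |
| SAP 8.3.1, SAGE-718 rollover | Not a TEAE: onset precedes 301 consent. Not pre-treatment either, since that also needs a post-consent onset. No category |

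The SAP's on-treatment and post-treatment classes also depend on onset date, so they do not pick the event up. Protocol 12.2.1 lets IP include placebo, so its starting point differs from the SAP's first SAGE-718 dose. That does not change the result here, because the worsening comes after both.

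**Step 2. Look for a rule elsewhere.** SAP Appendix B deals only with missing and partial dates. SAP 8.3.1 names listings for TEAEs, subsets of TEAEs, pre-treatment AEs and deaths. An uncategorised event in a SAGE-718 rollover has no named listing unless it is fatal, although Protocol 13.6.1 promises a listing of all AEs.

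**Step 3. Is the worsening a new record?** Protocol 12.2.5 asks for onset, resolution and intensity for each AE and does not say what to do when an AE worsens. If a new record with its own onset date is opened, the SAP rule counts it. If not, step 1 applies. The documents do not settle which.

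**Step 4. Size.** There is no stated figure to reproduce: the study is descriptive, and the documents give no AE rate, worsening count or parent-arm split. The planned number of rollovers (Protocol 7.2) is 128 + 28 = 156; the actual number is not given.

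Effect of *k* participants whose only qualifying event is such a worsening: 100 × *k* / 156.

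- *k* = 1: 0.64 points
- *k* = 3: 1.9 points
- *k* = 5: 3.2 points
- *k* = 10: 6.4 points

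For a plausible *k*, assume that a fraction *a* enter with an ongoing AE, a fraction *w* of those worsen, and a fraction *o* of those have no other TEAE. All three ranges are assumptions.

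| *a* | *w* | *o* | Worsened: 156 × *a* × *w* | Missed from proportion: × *o* | Points: 100 × *a* × *w* × *o* |
|---|---|---|---|---|---|
| 0.05 | 0.10 | 0.25 | 0.8 | 0.2 | 0.1 |
| 0.10 | 0.30 | 0.50 | 4.7 | 2.3 | 1.5 |
| 0.20 | 0.30 | 0.50 | 9.4 | 4.7 | 3.0 |

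The fourth column is the number who could be missing, or shown at too low a grade, in the preferred-term and maximum-severity tables. There, having another TEAE does not necessarily make up for the lost one.

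**The case against.** **The SAP follows the protocol's analysis section.** A reader might infer that the SAP departed from the protocol on its own. It did not: Protocol 13.6.1 is onset-only and the SAP stays close to it. The contradiction lies inside the protocol, and the SAP carries one side of it forward. This stands.

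**Loss is not shown.** A reader might take following an AE to resolution to mean that a worsened AE must keep its parent onset date. It does not: following the first event does not rule out a second record. Protocol 12.2.1 can be read as giving a worsening its own onset. Table 4, footnote f, dates worsening separately, though only for interim medical history in v2 Completers. Against this, the listing rule in Protocol 13.6.1 names onset and worsening as two different things. The point is therefore open, and the loss is conditional.

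**The exposed group is narrower than all pre-existing conditions.** Medical-history entries are not AE records, so a worsened one would more naturally be entered as a new AE with a post-consent onset. The risk is clearest for carried-over ongoing AEs. This stands.

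**Other outputs show part of the picture.** Ongoing parent AEs of placebo rollovers appear in the pre-treatment listing. The withdrawal endpoint is worded for AEs rather than TEAEs, and disposition gives the primary reason for withdrawal. The report is synoptic and descriptive, with no test to overturn. All of this limits the consequence. It does not restore the event to the TEAE proportion or severity tables, and it leaves room for disposition and TEAE-withdrawal counts to disagree.

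**The data may not support a correction.** Protocol 12.2.5 describes no dated grade changes within an AE record. This is a fair limit, and the fix allows for it.

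**Conclusion.** The point holds in conditional form. The two protocol sections disagree on whether worsening is treatment-emergent; the SAP takes the onset-only side without declaring it in 6.1 and does not say how a worsened carried-over AE is dated. If such an AE keeps its parent onset date, it is left out of the primary TEAE proportion and severity results.

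Two stronger conclusions are not supported. Ongoing parent AEs are not all classed as pre-treatment: that is true of placebo rollovers only, while those of SAGE-718 rollovers have no category. Nor do the documents support any particular rate of loss. The figure of 0.64 points per participant rests on the planned 156; the range of roughly 0.1 to 3 points rests on assumed fractions.

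This should be fixed, because the rule governs a primary endpoint in an all-rollover population and any error runs in one direction. Confidence is medium, because the recording practice cannot be seen.

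**What to change.** 1. Reconcile Protocol 12.2.1 with 13.6.1 on worsening.
2. In SAP 8.3.1, add to both rollover TEAE definitions: *or a pre-existing AE/condition that worsens on or after that date*. The date is the one each definition already uses.
3. Use the worsening date as onset and the post-worsening grade as severity where these are recorded. Where there is no dated change, compare the carried-over parent-study severity with the severity recorded in 301.
4. Limit the pre-treatment class to ongoing parent AEs that do not worsen.
5. Give ongoing parent AEs in SAGE-718 rollovers a category and a listing.
6. Record any retained difference from Protocol 12.2.1 in SAP 6.1.

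The cost is a few sentences before database lock and a record-level check of carried-over AEs. The TEAE count may rise slightly. If the eCRF already opens a new record at worsening, stating so in SAP 8.3.1 settles most of the point; items 1, 5 and 6 remain, and the pre-treatment clause should still make clear that the new record is not captured by it.

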Safety laboratory assessments ^k	X		X		X	X	X	X
Urine drug test		X ^f	X	X	X	X		X
Alcohol breath test		X ^f	X	X	X	X		X
Cigarette/tobacco use assessment		X ^f	X	X	X	X		X
Pregnancy test ^l	X		X		X	X	X	X
REDACTED								
C-SSRS (Since Last Visit)		X		X	X	X	X	X

Assessments	Carry-over Results of the Last Assessments from Parent Studies when Applicable ^{a,f}	Treatment Period						
		Day 1	Day 30 (±7 days)	Day 60 (±7 days)	Day 90 (±7 days)	Day 180 (±14 days)	Day 270 (±14 days)	Day 365 (±14 days) ^b
UHDRS ^p	X							
MoCA	X							
IP self-administration ^w					X (once daily in the morning)			
IP dispensation ^x		X	X	X	X	X	X	X
IP accountability/return ^y			X	X	X	X	X	X
IP adherence monitoring					X			
AEs/SAEs ^z					X			
Prior and concomitant medications and procedures/therapies ^{aa}					X			

Abbreviations: AE = adverse event, CAG = cytosine-adenine-guanine trinucleotide repeat within the huntingtin gene, [REDACTED]; COVID-19 = coronavirus disease 2019; C-SSRS = Columbia–Suicide Severity Rating Scale; ECG = electrocardiogram; eCRF = electronic Case Report Form, FSH = follicle-stimulating hormone; [REDACTED]; HD = Huntington's Disease; [REDACTED]; HIV = human immunodeficiency virus; IP = investigational product; MoCA = Montreal Cognitive Assessment; [REDACTED]; SAE = serious adverse event; [REDACTED]; UHDRS = Unified Huntington's Disease Rating Scale; [REDACTED].

NOTE: Any additional parent study data needed to support the 718-CIH-301 data or analyses will be carried over from the applicable parent study.

- ^a The carryover assessments constitute the baseline/screening assessments for this extension study.
- ^b Participants who have completed their Day 395 visit under Protocol Version 2 and wish to continue participation under Protocol Version 3 or higher (“718-CIH-301 v2 Completers”) will return to the site for a Re-Qualification Visit ([Table 4](#)) up to 28 days prior to resuming IP at their Next Scheduled Study Treatment Visit (relative to the date of their Day 1 visit, see [Table 5](#)).
- ^c Both participants and study partners (if applicable) will be consented on Day 1. A legally authorized representative may consent on behalf of participants who are not capable of providing informed consent in the opinion of the investigator. [REDACTED]

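### SAP 8.3.1: the AE phase boundaries do not meet, so an AE after consent but before the first dose can be a TEAE with no phase (SAGE-718 rollovers) or, on one reading, fall in no class or AE listing (placebo rollovers)

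*SAP*

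**What the plan says.** SAP 8.3.1 defines AE classes separately by parent-study treatment.

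- **SAGE-718 rollovers.** "TEAE is defined as an AE with onset on or after the ICF sign off in this protocol". The pre-treatment class is narrower at both ends: "Pre-treatment AE is defined as an AE with onset after ICF sign off date in this protocol and before the first dose date of IP". The next class starts at a clock time: "On-treatment TEAE is defined as an AE with onset on or after first IP dose date/time".
- **Placebo rollovers.** "TEAE is defined as an AE with onset on or after the first dose of SAGE-718 in this protocol". Their pre-treatment class takes AEs with onset before that dose and "after ICF sign off date in this protocol or ongoing AE from parent study".
- **Both.** Post-treatment starts 31 days after the last dose date.

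The overall TEAE summary in the same section counts participants with any TEAE and then splits them into pre-treatment, on-treatment and post-treatment. On listings the section says "All TEAEs through the end of the study will be listed by participant. Separate listings of pre-treatment AE". It then names listings of treatment-emergent SAEs, of TEAEs leading to discontinuation, withdrawal or interruption, and of deaths.

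For Cohort 1, Protocol Table 3, footnote c, states "Both participants and study partners (if applicable) will be consented on Day 1" (repeated in SAP Table 6). SAP 8.1.1 defines Day 1 as the date of first dose. Protocol 13.6.1 commits to more than the SAP's listings: "All AEs and SAEs (including those with onset or worsening before the start of IP) through the end of the study will be listed".

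**The concern.** AE collection begins when consent is completed, and Protocol 12.2.5 has the investigator record onset date and time. An AE between consent and first dose is therefore collected and can be placed in time. The three phases ought to cover that interval without a hole, and they do not. The pre-treatment class opens after the consent date rather than on it. For SAGE-718 rollovers it also closes at the start of the first-dose date, while on-treatment opens only at the dose itself.

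Two things are at stake. A participant can appear in the any-TEAE row and in none of the phase rows beneath it. And an AE or SAE in a placebo rollover could be missing from every AE listing that the SAP plans. The interval is short but not idle: in Cohort 1 all Day 1 assessments are to be done before dosing (Protocol Table 3, footnote w), so study procedures fall inside it. Cohort 3 was not enrolled (SAP 6.1), so both cohorts being reported are affected.

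**Working it through.** The plan gives no figure to reproduce. The check applies the SAP 8.3.1 rules to each possible onset, with the consent boundary read by date or by clock time, and the placebo rollovers' first-dose boundary read the same two ways.

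**Step 1. Cohort 1, SAGE-718 rollovers.** Let D be Day 1. Consent date = D and first-dose date = D. Pre-treatment needs onset date > D and < D, which no date satisfies. Reading consent by clock time does not help, because the end of the class is still the first-dose date. The class is empty on every reading.

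**Step 2. All cases with onset after consent.**

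| Onset | SAGE-718 rollover | Placebo rollover |
|---|---|---|
| Cohort 1, Day 1, pre-dose | TEAE, no phase (every reading); in TEAE listing | Consent by date, dose by time: no class, no AE listing. Both by time: pre-treatment. Dose by date: on-treatment TEAE |
| Cohort 2, consent day | TEAE, listed. Consent by date: no phase. By time: pre-treatment | Consent by date: no class, no AE listing. By time: pre-treatment |
| Cohort 2, between consent day and Day 1 | TEAE, pre-treatment | Pre-treatment |
| Cohort 2, Day 1, pre-dose | TEAE, no phase (every reading); in TEAE listing | Dose by time: pre-treatment. Dose by date: on-treatment TEAE |
| Either cohort, Day 1, post-dose | TEAE, on-treatment | TEAE, on-treatment |

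On the Cohort 2 consent day the way first dose is read makes no difference, because dosing is on a later date.

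**Step 3. Listings.** A placebo-rollover AE that is neither a TEAE nor pre-treatment enters none of the listings named in SAP 8.3.1 except the death listing, which is not limited to TEAEs. The general promise in SAP 8.1 covers data that support tables and figures, and this event supports none. Protocol 13.6.1 requires it to be listed, and SAP 6.1 does not name that listing as dropped.

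**Step 4. Size.** Inputs: 156 expected rollovers (Protocol 13.8); an assumed 1 to 4 AEs per participant-year; an assumed 3 hours between consent and dose. The documents give neither the rate nor the interval.

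- Full consent day, all rollovers: 156 × 1 / 365.25 = 0.43; 156 × 2 / 365.25 = 0.85; 156 × 4 / 365.25 = 1.71.
- Three-hour window: × 3/24 gives 0.05, 0.11 and 0.21.

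Both lines pool the two parent arms. The placebo share is smaller; the documents give no arm split.

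**Step 5. After the change.** If pre-treatment runs from consent (inclusive) to the first-dose date and time in both arms, every post-consent, pre-dose AE in the table is pre-treatment and listed. In SAGE-718 rollovers it also stays a TEAE.

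**The case against.** The strongest reply is that this is a wording slip with little effect.

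- **The unlisted placebo case depends on the reading.** In Cohort 1 it needs consent read by date and first dose by clock time. The placebo text says first dose without adding a time, so a programmer could read it by date and get an on-treatment TEAE. This stands: the result is conditional. The literal reading is still well supported. The consent boundary is worded as a date, and the placebo on-treatment bullet notes that time does not matter for the end of the period, which implies that it matters at the start. That one event could come out as unlisted, pre-treatment or on-treatment is itself a reason to settle the wording.
- **The phase rows need not add up anyway.** They count participants, and one participant can have TEAEs in several phases. This stands. A visible gap needs a SAGE-718 rollover whose only TEAE began before dosing in the gap.
- **Nothing is lost to safety reporting.** All post-consent AEs are reported to the sponsor, and SAEs go on a form within 24 hours (Protocol 12.2.1, 12.2.2 and 12.2.6). This stands. The gap is in the SAP's outputs, not in safety capture.

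A reader might also infer that the whole pre-treatment class is empty in Cohort 1, or that every consent-day AE goes unlisted. The documents support neither. The placebo definition also takes AEs ongoing from the parent study, and the SAGE-718 rollovers' events are in the listing of all TEAEs.

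**Conclusion.** The point holds as a small error in a stated rule. For SAGE-718 rollovers the phase gap on Day 1 before dosing exists in both cohorts on any reading; on the Cohort 2 consent day it depends on reading consent by date. For placebo rollovers, the missing class and listing depend on reading consent by date and, in Cohort 1, first dose by clock time as well. On that reading the SAP falls short of Protocol 13.6.1.

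On the assumed rates, about 0.05 to 0.2 events are expected in a 3-hour window, and at most 0.4 to 1.7 over a full consent day for all 156 rollovers. No safety conclusion is likely to change.

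It would be wrong to infer that the TEAE endpoint itself is misstated. With first dose read by clock time, a pre-dose AE in a placebo rollover is properly not a TEAE, and one in a SAGE-718 rollover is counted as the SAP intends. TEAE incidence and severity tables stay as they are; only the phase rows and the pre-treatment listing change.

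**What to change.** In both pre-treatment definitions in SAP 8.3.1, require onset on or after ICF sign-off (by date and time where available) and before the first-dose date and time of IP. Keep the placebo clause that adds AEs ongoing from the parent study. Add one sentence saying that the first-dose boundary is by date and time for both parent arms. If any program has applied the placebo boundary by date, that sentence would move a Day 1 pre-dose AE from on-treatment TEAE to pre-treatment, so check for such cases when making the change.

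The cost is two phrases, one sentence and about one line of programming. No new data are needed, because onset date and time are already collected.
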